In the 97 total patients treated in the PSI, IRI and RTI studies there has not been the need to abort the use of the novel instrumentation, nor has there been a complication during or after surgery related to the technology. Moreover the objective data of post-operative implant position has proven the PSI, IRI and RTI technology to be better than control groups.

Study Design

Methods

Continuing our work, we propose a randomized clinical trial to evaluate the accuracy of glenoid implant placement comparing four groups of patients. Group 1 consists of 3D imaging and computer-generated surgical planning using standard DePuy instrumentation for placement of the glenoid implant. This group is considered the standard of care group (SOC). Group 2 consists of 3D imaging and computer-generated surgical planning, with use of a SmartBone to trial the standard DePuy instrumentation. (Group 2 is Group 1 with addition of the use of a SmartBone.) Group 3 consists of 3D imaging and computer-generated surgical planning, with use of the IRI technology including a SmartBone, but with metal legs instead of plastic legs, which were used in the IRB#13-652 study. Group 4 consists of 3D imaging and computer-generated surgical planning, with use of the RTI technology including a SmartBone.

We will measure implant placement with RSA (bi-planar x-rays) and 3D CT imaging. We will measure pre-operative bone quality using quantitative CT to measure trabecular bone volume and correlate these findings with bone samples removed from the humeral head and measured by microCT, and mechanical testing of the bone samples. These bone samples will be obtained as part of the routine preparation of the humeral head for implant placement. This bone tissue is normally removed and discarded as part of the standard of care for preparation of the bone for placement of the humeral implant. We have performed all of the work required to define both the safety of all components of the proposed study in the completed PSI study and the ongoing IRI and RTI studies (#s 10-582, 12-997 and 13-652, respectively). Since application to the IRB for study of the IRI technology Custom Orthopaedic Solutions (Cleveland Clinic NewCo) has received in April 2013 FDA approval for this technology.

Glenoid Instrumentation and Pre-operative planning

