All patients will receive a Standard of Care pre-operative CT scan that will be used for the 3D imaging-based computer modeling to determine the best location for the glenoid implant. The surgeon will approve the surgical plan, and the printed surgical plan will be available in the OR for consultation by the surgeon. The four groups differ in the way that this pre-operative plan is used during the surgical procedure to position the glenoid implant.

Group 1 (SOC, control group):

In this group the surgeon will use standard DePuy instrumentation provided with the implant to implement the pre-operative surgical plan.

Group 2 (SOC plus SmartBone):

In this group the surgeon will use standard DePuy instrumentation provided with the implant and the use of a patient-specific SmartBone that contains a guide pin inserted into the SmartBone that mimics the pre-operative surgical plan to implement the pre-operative surgical plan.

Group 3 (SOC plus IRI with metal legs and SmartBone):

This group is a variation on the IRI study protocol (IRB #12-997). In the IRI study, the IRI tool has plastic legs of different lengths to conform to the contours of the patient's glenoid anatomy, which is reproduced in the SmartBone model. In group 3, the legs of the IRI tool will be fabricated from metal.

Group 4 (SOC plus RTI and SmartBone):

This group is identical to the RTI study protocol (IRB #13-652). In group 4, PMMA bone cement will be used to create a cognate mold of the patient's glenoid anatomy, which is reproduced in the SmartBone model, to implement the pre-operative surgical plan.

Group 5 (SOC plus IRI using SmartBase instead of SmartBone):

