This group is a variation of Group 3 of this study. We have designed a new component, "SmartBase", which takes the place of the 3D-printed SmartBone. The SmartBase is a metal base with adjustable metal tabs that support each of IRI legs. In the 3D modeling software, an impact detection function is used to place the IRI tool on the computer model of the patient's glenoid, and the appropriate metal leg is chosen for each slot of the IRI so that the IRI is in the correct position to place the guidepin in the position dictated by the pre-operative plan. The computer software also calculates the height from the tip of the IRI to the point of contact on the computer model of the patient's glenoid for each of the legs. These distances are included in the pre-operative plan provided to the surgeon. In the operating room, the metal tabs of the SmartBase are adjusted to the proper height for each of the corresponding legs of the IRI. The surgeon then uses the IRI to drill the guidepin in the correct position and orientation into the patient's glenoid.

This method has been shown to be equivalent to the IRI group in pre-clinical testing. The rationale for testing this methodology in the current clinical trial is that the SmartBase does not require fabrication of a sterile SmartBone, which will provide a much faster delivery of the patient-specific instrument.

In all enrolled cases the surgeon will have full control to define the optimal position of the guide pin and the final implant. The surgeon can default to standard of care technology in any case in which the IRI or RTI technology cannot be used or results in guide pin position that, in his best medical opinion, is not consistent with the pre-operative plan. Therefore, the surgeon is in full control of all intra-operative decision making and execution of the procedure.

Measurement of Implant Position

Post-operatively we will obtain a CT scan with metal artifact reduction technology within the first few weeks after surgery and will generally obtain this scan prior to discharge from the hospital. A second CT scan will be obtained at two years after surgery. We have used these methods of 3D CT imaging to determine implant position in several prior studies. We have defined the accuracy of these measurements using first generation techniques to be within 1 millimeter and 3 degrees. We anticipate that the accuracy of these second generation imaging techniques will be improved from our earlier work.

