To assess bone quality and its effect on glenoid component loosening, we will take humeral head bone samples from all patients. These bone samples will be assessed by microCT to measure trabecular bone volume and connectivity as well as by mechanical testing. These data will be correlated with the trabecular bone volume of the glenoid defined by the pre-operative CT scans. In addition all bone quality measurements will be correlated with CT scan imaging of the glenoid at the time of surgery and at two year follow up.

In order to acquire consistent information on bone quality across the patients, a custom-made calibration phantom object will be located between the CT bed and the patient. The phantom object consists of three cylindrical rods, each with a known density of hydroxyapatite (0, 500, and 1,000 mgHA/cm³) embedded in a soft foam block. The grey-level of pixel from the rods will be used to calibrate the Hounsfield units and the corresponding bone density using custom-written software.

Patient Enrollment

The proposed clinical trial will randomly enroll patients indicated for standard of care anatomic total shoulder arthroplasty into one of the four treatment groups. Our goal is to have 20 subjects in each treatment group. To accomplish this goal, we will enroll up to 120 subjects to control for subject withdrawal after enrollment. To enroll at least 20 patients into each group, including Group 5 (SmartBase), new randomization envelopes will be generated that start at number 34. The distribution of patients into Groups 1 – 4 at the time that Group 5 was begun is:

Group 1: 8
Group 2: 7
Group 3: 7
Group 4: 10

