Post-operatively, all patients will receive a CT with MAR and RSA (if chosen) within 3 weeks of surgery. This will be a CT Scan performed with the patients arm by the side in a supine position using metal artifact reduction techniques. In addition patients will receive a second CT scan RSA imaging, provided they originally got RSA, performed 2 to 3 years (\pm 2 months) after surgery. The second CT scan will be performed with MAR techniques and with the patient in the arm by the side position again using metal artifact reduction techniques. We have shown that in a small number of patients the glenoid component can shift in position within the first 3-6 months after surgery making the first CT Scan more accurate for implant position. The images obtained from the post-operative CT scans are placed back into the surgical software and the 3D reconstruction of the post-operative

scapula with the implants is compared to the pre-operative plan. Using measurement tools within the software, developed at Cleveland Clinic, we will compare the position of the actual glenoid component placed in the patient with the desired position specified by the pre-operative plan. The use and validation of these imaging methods to precisely measure implant position has been performed at the Cleveland Clinic in a prior IRB approved studies (IRBs 10-582, 12-997 and 13-652).

Pre-operatively, the high resolution quantitative CT will measure volumetric bone mineral density and the trabecular network of the glenoid. When available, this will be applied to the pre-operative CT for those patients at Main Campus. Patients who have their pre-operative CT completed at non-Main Campus facilities will have the standard of care pre-operative CT. This will be done at the same visit for the standard of care pre-operative CT. Micro CT imaging, which creates a 3D reconstruction of the fine bone structure, in addition to microarchitecture analysis and mechanical testing, will allow assessment of the bone tissue taken from the bone core sample. Between the preoperative imaging and the bone tissue analysis, we will have data to properly determine the quality of the bone stock surrounding the implant. Further correlating this with RSA and 3D CT imaging of implant movement, we can fully develop the cause and effect of bone quality on glenoid component loosening.

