All analyses will be done using R software (version 3.0.0, Vienna, Austria). A significance level of 5% will be used for all testing.

Data Sheets

Clinical data collected pre- and post-operatively will be passive and active range of motion, manual muscle strength testing and shoulder functional scores, and co-morbidities, all of which are standard of care. Post-operative data will be collected at two years (\pm 2 months) after surgery. We will collect at the time of surgery the implant used, the time for surgical care glenoid exposure to end of pin placement. The implant used, the surgical instruments used and any comments from the surgeon as to the ease of use and accuracy of the instruments. Verbatim comments will be solicited and recorded by a research assistant attending all surgical procedures.

Pre-operative imaging data will include: glenoid version and inclination, estimated pre -morbid inclination, version and depth of glenoid bone loss using the glenoid vault model, preferred implant type inclination and version.

Post-operative implant placement to desired location will be defined for the location of the center peg of the implant in the superior/inferior (SI), anterior/posterior (AP) and medial/lateral (ML) dimension in millimeters and the trajectory of the center peg vs plan in version and inclination. The location of the implant in relation to the joint line as measured by the glenoid vault model will be measured in millimeters. Back side contact of the implant to the bone will be measured as a surface area in direct contact with the bone and any lucent lines around the implant pegs will be measured. Peg perforation and the location of the peg perforation will be recorded. The tantalum beads within each implant will be measured for translational or rotational movement.

Changes in implant position from post-operative CT scan (CT 1) vs the first post-operative CT scan (CT 2) will be correlated with back side seating, implant type, medialization of the joint line and peg perforation and severity of the post-operative pathology.

Study data will be collected and managed using REDCap (Research Electronic Data Capture). Tracking data will be stored in an Excel spreadsheet, which will exist only on password-protected computers or on restricted-access CCF servers. Only study personnel will have access to the data.

Adverse Events and Data Monitoring Committee (DMC):

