A Data Monitoring Committee will not be used. Patient safety will be protected by following surgical standards of care. The IRB will be notified in writing of any adverse clinical event related to the use of the IRI or the standard instrumentation. Adverse events include excessive bleeding, infection, fracture nerve injury or need for revision surgery during the term of this study which is expected to be approximately 1 year from the time of surgery.

Consent:

During a pre-operative office visit the patient's primary surgeon will conduct the consent interview, obtain the signed Informed Consent, witness, sign and send the original to the study coordinator. A copy of each Informed Consent form will be sent home with the patient for their records. Informed Consent forms may also be sent to patients if they are located out of town. Research personnel will send multiple copies of the Informed Consent along with a self-addressed stamped envelope to the patient home for review, signature and return. Prior to the patient signing the Informed Consent, research personnel or the surgeon will call the patient to discuss the study, answer questions and ensure that the patient fully understands all aspects of the study. After being contacted, the patient may then sign and send back the informed consent.

Funding Sources and Budget

Funding source: State of Ohio Biomedical Research and Development Grant- Products to Improve Orthopaedic Patient Outcomes (PIOPO)- [name], PhD, Principle Investigator.

References:

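### The safety section expects a study term of about 1 year although assessments are planned at two years or later, and its IRB notification sentence does not name the RTI mold or the bone beads

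*Combined protocol and SAP*

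**What the plan says.** **Term.** The section on adverse events and the DMC gives a list of adverse events whose last item is revision surgery, followed by the phrase "during the term of this study which is expected to be approximately 1 year from the time of surgery". Other sections plan later assessments:

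- Measurement of Implant Position: "A second CT scan will be obtained at two years after surgery".
- Bone Quality Measurements: the bone measurements "will be correlated with CT scan imaging of the glenoid at the time of surgery and at two year follow up".
- Detailed Study Design: the second CT, with RSA for patients "provided they originally got RSA, performed 2 to 3 years" after surgery, with a window of plus or minus 2 months.
- Data Sheets: "Post-operative data will be collected at two years", again plus or minus 2 months.

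**Notification.** The safety section undertakes to notify the IRB in writing of "any adverse clinical event related to the use of the IRI or the standard instrumentation". This sentence carries no time limit. The section also says that there is no monitoring committee and that patient safety rests on surgical standards of care.

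**Components.** Study Design defines the arms; "Group 2 is Group 1 with addition of the use of a SmartBone". Glenoid Instrumentation describes that addition as "the use of a patient-specific SmartBone that contains a guide pin inserted into the SmartBone". Group 3 uses the IRI with a SmartBone, Group 4 the RTI cement mold formed on a SmartBone, and Group 5 the IRI with a SmartBase. Detailed Study Design places four to five tantalum beads in bone, and Patient Enrollment counts bead placement among the trial's departures from usual care.

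**The concern.** The one time reference attached to adverse events is about half the nominal two-year follow-up. Read literally, it leaves open whether a late revision belongs to the adverse event list, although the protocol follows patients to two years or more partly to study glenoid loosening.

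The notification sentence raises a different question. One randomized arm is defined by a device that the sentence does not name, and the bone beads are a study procedure that it does not name either. Someone applying the protocol cannot tell whether an event attributed specifically to the mold or to a bone bead must be notified. With no monitoring committee, this is the only rule for reporting adverse events that the protocol states, so it should match the protocol's own schedule and components.

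**Working it through.** No sample-size, power or alpha formula applies. The check compares the stated term with the planned windows, then the named devices with the devices in use.

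**1. Term**

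Inputs: expected term 12 months (safety section); clinical data 24 months ± 2 (Data Sheets); second CT 24 to 36 months ± 2 (Detailed Study Design). I assume that the ± 2 months applies at both ends of the 2 to 3 year range.

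| Assessment | Window (months) | Months after the 12-month term |
|---|---|---|
| Clinical data | 24 − 2 = 22 to 24 + 2 = 26 | 22 − 12 = 10 to 26 − 12 = 14 |
| Second CT, and RSA where done | 24 − 2 = 22 to 36 + 2 = 38 | 22 − 12 = 10 to 38 − 12 = 26 |

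Without the window, the second CT falls at 24 to 36 months, which is 12 to 24 months after the stated term. Even the earliest permitted late visit, at 22 months, cannot be read as approximately 1 year.

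**2. What the time phrase governs**

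It may qualify the whole list or only its last item. That item is revision surgery, so the mismatch affects revision on either reading. The phrase does not qualify the notification sentence, which comes before it and stands alone.

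**3. Devices named against devices used**

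Allocated when Group 5 began, plus new envelopes (Patient Enrollment): 8 + 12 = 20, 7 + 13 = 20, 7 + 13 = 20, 10 + 10 = 20, and 0 + 20 = 20, a total of 100.

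| Group | Study-specific instrument | Named in the notification sentence? | Patients |
|---|---|---|---|
| 1 | none (standard instrumentation) | yes | 20 |
| 2 | SmartBone | arguable: it is used to trial the standard instrumentation, which is named | 20 |
| 3 | IRI with SmartBone | IRI yes; SmartBone arguable, as it is used with the IRI | 20 |
| 4 | RTI mold formed on a SmartBone | no, although events from the standard instrumentation used after pin placement are covered | 20 |
| 5 | IRI with SmartBase | IRI yes; SmartBase arguable, as it is used with the IRI | 20 |

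The clear gap is Group 4's instrument: 20 of 100 patients, of whom 10 were among the 8 + 7 + 7 + 10 = 32 already allocated when Group 5 began.

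**4. Bone beads**

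The notification sentence does not name them. The number of patients who receive them is not stated. Detailed Study Design sets no limit on patients, while Measurement of Implant Position limits the RSA imaging that the beads serve to at most 20 subjects. Depending on the assumption, the number runs from at most 20 (RSA subjects only) to all 100. Detailed Study Design calls beads in the glenoid implant standard of care at the site, but does not say so of the beads in bone.

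**The case against.** **The term point has little practical consequence.** The 1 year is only an expectation, the list is worded as open-ended, and no analysis uses it: Outcome Measures and Data Analysis contain no adverse event comparison. This stands, and it limits the point to a contradiction to be reconciled. It does not remove the contradiction, because no reading turns 22 months or later into about 1 year.

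**A reader might infer that IRB notification stops at 12 months.** The documents do not support that, since the notification sentence has no time limit.

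**Safety is protected in other ways.** The safety section relies on surgical standards of care. The IRI and RTI technology sections record reasons for device failure, and Data Sheets collects surgeon comments and two-year data. A reader might infer that late or device-related problems would go unseen; these provisions speak against that. None of them, however, is a rule on which events are notified.

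**The scope gap could be overstated.** A reader might count Groups 2 and 4 together as 40 of 100 without cover, or stretch this to 50 by taking 25 per group from Sample Size. Neither holds. Cover in Group 2 is arguable, because Study Design has the SmartBone used to trial the named standard instrumentation. Twenty-five in each of five groups would be 5 × 25 = 125, above the stated maximum of 120. Group 4 patients do have cover for events from standard instrumentation.

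**Recording events to the last planned visit would miss some patients.** Patient Enrollment and the IRI and RTI technology sections exclude patients in whom the device was not used, or the pin was changed without it, and give them no post-operative imaging. For them the last planned assessment is undefined. This stands, and the fix has to address it.

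**Conclusion.** Two separate points hold.

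- **Term.** The expected term of about 12 months contradicts the protocol's own follow-up of 22 to 26 months for clinical data and 22 to 38 months for the second CT. The gap is 10 to 26 months and bears at least on revision surgery. The upper figure rests on the 2 to 3 year schedule in Detailed Study Design; Measurement of Implant Position gives two years only.
- **Notification.** The sentence omits the RTI mold (20 of 100 patients under the envelope plan) and the bone beads (number not stated). Cover for the SmartBone in Groups 2 and 3 and for the SmartBase in Group 5 is arguable rather than absent. The counts are patients exposed to an unnamed component, not patients without any cover.

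A reader might go on to infer bias in the placement comparison or a loss of power. Nothing in the documents supports either, and they give no event rate from which an effect could be derived. The point should be corrected because the safety text does not match the trial it governs and correction is cheap.

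**What to change.** 1. Reconcile the expected term in the safety section with the follow-up schedule in Measurement of Implant Position, Bone Quality Measurements, Detailed Study Design and Data Sheets. Settle at the same time whether the second CT is at two years or at 2 to 3 years.
2. State that adverse events, including revision surgery, are recorded over the reconciled term for all randomized patients. Say how this applies to patients excluded from post-operative imaging under Patient Enrollment and the IRI and RTI technology sections.
3. Extend the notification sentence to all study-specific components (IRI, RTI, SmartBone, SmartBase and bead placement) as well as the standard instrumentation.

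The cost is amendment wording, an event check at assessments already planned for most patients, a separate follow-up check for the excluded patients, and slightly more event reporting.
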